- **3.5.3. Subgroup Analyses.** Moderating effects will be conducted to determine whether delivery mode (telemedicine vs. in-person) or agent (specialist vs. non-specialist) have differential effects as a function of initial severity, whether mothers who receive antenatal treatment have lower depressive symptoms at 12-months post-enrollment than those who receive postnatal treatment; and whether children whose mothers receive the antenatal treatment have higher child development scores at 6-24 months post child birth than those children whose mothers receive postnatal treatment.
- **3.5.3.1.** Clinical Severity. Tests of moderation will be conducted to determine whether delivery mode (telemedicine vs. in-person) or agent (specialist vs. non-specialist) influence mothers who are severely depressed (EPDS>19). We expect 10 to 15% of our sample to be severely depressed (EPDS>19). A 2-group comparison with 75 per group and an assumed mean EPDS score of 20.0 (SD=7.0 , will provide 80% power, with an alpha of 0.05, to detect a mean change of 2.3 or greater. Our current sample size including those within severity subgroups described above will be adequately powered to detect medium effect size differences of HTE of symptom severity between groups. This indicates that we have adequate power for clinically meaningful tests. The two groups' (specialist vs non-specialist) EPDS scores at 3-months will be compared using a two-sided two-sample t-test. Change in EPDS score over time (baseline and every 3 months, post-randomization) will also be compared using linear mixed models. We will also examine this on anxiety symptoms at 3-months post randomization.

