1.1. Principal Research Objectives

The primary objectives of this trial are to:

- Examine if a brief, BA psychological treatment delivered by non-specialist providers (NSP) is as effective in treating perinatal depressive symptoms as specialist-delivered treatment* (*Primary Aim 1*); and
- Examine if a brief BA psychological treatment delivered through telemedicine (TM) is as effective in treating perinatal depressive symptoms as in-person treatment (IP; *Primary Aim 2*)*.

*Note: 'as effective' is the language that we used in the PCORI submission and what PCORI would like to see when they review this document. After consultations with several statistical experts, we will cater the language accordingly for the audience e.g., use 'non-inferior' for academic audiences and the current language for lay audiences.

The primary hypotheses are that among mothers with depressive and anxiety symptoms, psychological treatment delivered by NSPs will be as effective as treatment delivered by specialist providers. In addition, psychological treatment delivered via TM will be as effective as in-person treatment at 3-months, post randomization.

[figure not shown]
The secondary objectives are to:

- Examine the aforementioned questions for anxiety symptoms at 3-months post randomization (*Secondary Aim 1*);
- Assess moderating effects of clinical severity (mild, moderate and severe) on the comparative effectiveness of the two delivery modes on depressive and anxiety symptoms at 3-, 6- and 12-months post randomization (*Secondary Aim 2*);
- Explore whether the timing of the treatment (antenatal vs. postnatal) influences depressive and anxiety symptoms at 12-months post-randomization, and separately, on child mental development at 6 to 24 months post childbirth (*Secondary Aim 3*); and
- Conduct a process evaluation, i.e., identify the underlying processes related to delivery and scalability of a brief psychological treatment for perinatal depressive and anxiety symptoms from a multi-stakeholder perspective, including relevant barriers and facilitators (*Secondary Aim 4*).

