1.6.2. Primary Aim 2 (Telemedicine vs. In-Person) Comparison

The primary outcome measure is an EPDS mean score at 3 months post-randomization. The sample size calculation is based on an EPDS mean estimate of 7.93 (SD=4.68)³⁰. Using a non-inferiority margin of 13% (i.e., EPDS score of 1.03 in relation to the mean), and an alpha=0.05, we require an additional 268 IP participants ([Table 4](#)).

Table 4: Non-inferiority margin in relation to sample size for Phase 3 comparisons

Non-inferiority margin	Power	Sample size per primary question	Total sample size + 10% dropout*	Total sample size + 20% dropout
10%	80%	431	958	1078
13%	80%	241	536 (268 per group)	604
14%	80%	221	492 (246 per group)	556

*Current dropout rates are <10% at primary outcome of 3-months post-randomization

When combined with the 958 TM participants, this yields a total study sample size of N=1,226 which accounts for 10% loss to follow-up ([Table 5](#)).

Table 5: Primary aims and required sample sizes

Primary Aim [¥]	Non-inferiority Margin	Power	Required sample size + 10% drop out
SP vs. NSP [¥]	10%	88%	958 telemedicine
IP vs. Telemedicine	13%	80%	268 in-person*
	Total		N=1226*

[¥]We acknowledge that the in-person sample is contained in the first hypothesis. This will result in the SP vs NSP comparison having up to 88% power. *We will over-recruit to account for protocol deviations where participants were switched from in-person to telemedicine due to the COVID-19 pandemic.

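### Protocol 3.5.3.1 claims adequate power for medium-size effect heterogeneity by severity without an interaction calculation, and its supporting two-group figure gives about 52% power where it states 80%

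*Protocol*

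**What the plan says.** Protocol 3.5.3.1 opens with the planned analysis: "Tests of moderation will be conducted to determine whether delivery mode (telemedicine vs. in-person) or agent (specialist vs. non-specialist) influence mothers who are severely depressed". On the size of that group it says "We expect 10 to 15% of our sample to be severely depressed (EPDS>19"). The calculation follows: "A 2-group comparison with 75 per group and an assumed mean EPDS score of 20.0 (SD=7.0") "will provide 80% power, with an alpha of 0.05, to detect a mean change of 2.3 or greater". From this the paragraph concludes that the sample "will be adequately powered to detect medium effect size differences of HTE of symptom severity between groups". It then names a two-sided 3-month t-test for specialist versus non-specialist, and linear mixed models for change over time.

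SAP 1.1 states Secondary Aim 2 for mode: "Assess moderating effects of clinical severity (mild, moderate and severe) on the comparative effectiveness of the two delivery modes", at 3, 6 and 12 months. SAP 3.4.2.3 assigns it to linear mixed models and sizes it at 44 women, using a 10% non-inferiority margin.

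On allocation, SAP 1.6.2 says "we require an additional 268 IP participants" to set beside 958 in telemedicine, total 1,226 with 10% loss included. Protocol 2.6 has the same figures. SAP 1.5 stops in-person randomization once those arms are full.

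**The concern.** Moderation is a difference of differences: the arm effect in severe women minus the arm effect in the others. Its variance has four components, one for each severity-by-arm cell, and the smallest cell dominates. A comparison of two equal halves of the severe group leaves out the non-severe cells. For mode it also assumes a balance that the recruitment plan rules out, since 75 severe in-person women cannot be expected from 268 when 10-15% are severe.

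SAP Secondary Aim 2 asks whether the relative effect of the two modes depends on severity. If the plan says beforehand that power is adequate, a non-significant interaction is easily taken to mean that telemedicine works equally well in severely depressed women. The stated power should therefore belong to the test that will be run.

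**Working it through.** **1. The plan's own figure.** Inputs from Protocol 3.5.3.1: 75 per group, SD 7.0, difference 2.3, alpha 0.05, two-sided.

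- SE = 7.0 × √(2/75) = 1.143, and 2.3/1.143 = 2.012.
- Power = Φ(2.012 − 1.960) = 52% (51.6% with the t distribution; 64% if one-sided).
- Difference detectable with 80% power = (1.960 + 0.842) × 1.143 = 3.2 points.
- Number per group for 2.3 points = 2 × (2.802 × 7.0/2.3)² = 145.4, so 146.

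The stated 80% is not reproduced. A one-sample or paired formula comes close: SE = 7.0/√75 = 0.808, power 81% (80% with t). That is not the two-group design described.

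**2. Cell sizes for mode.** After 10% loss, 268 × 0.9 = 241.2 in person and 958 × 0.9 = 862.2 in telemedicine.

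| Severe share | Severe IP | Severe TM | Other IP | Other TM |
|---|---|---|---|---|
| 10% | 24.1 | 86.2 | 217.1 | 776.0 |
| 15% | 36.2 | 129.3 | 205.0 | 732.9 |

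**3. Interaction power.** Assumptions: medium = 0.5 SD (the documents do not define it; Protocol 3.5.3.2 calls 0.3 small), common SD, severe versus all others, unadjusted 3-month EPDS, two-sided 0.05.

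SE in SD units = √(1/n₁ + 1/n₂ + 1/n₃ + 1/n₄); power = Φ(0.5/SE − 1.960); effect detectable at 80% power = 2.802 × SE. The provider rows take a 1:1 split of 1,226 × 0.9 = 1,103.

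| Contrast | Severe share | SE | Power at 0.5 SD | Detectable at 80% |
|---|---|---|---|---|
| Mode | 10% | 0.243 | 54% | 0.68 SD |
| Mode | 15% | 0.204 | 69% | 0.57 SD |
| Provider | 10% | 0.201 | 70% | 0.56 SD |
| Provider | 15% | 0.169 | 84% | 0.47 SD |

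With no loss, mode power is 58-73%; with the 20% loss in Protocol 3.2 it is 49-64%.

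**4. What could raise the mode figure** (10% loss, from 10% to 15% severe).

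- Adjustment for entry EPDS multiplies the SE by √(1 − ρ²): 58-73% at ρ = 0.3, 66-81% at 0.5, 82-93% at 0.7.
- Averaging the effect over three visits at within-woman correlation 0.5, with no further loss, multiplies the SE by √(2/3): 71-85%.

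**5. Which cause.** If mode were split equally, its power would equal the provider figure, 70-84%. So at 10% severe the rarity of severe women alone keeps power below 80%, and the 268/958 split lowers it further.

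**6. Source of the optimism.** An equal comparison of 75 and 75 at 0.5 SD has 86% power. The claim about medium effects fits that simple comparison and does not carry over to the interaction.

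**7. The SAP's 44.** SAP 3.4.2.3 gives no SD, contrast or interaction size for it, and a non-inferiority margin does not size a moderation test. In SAP Table 3, a 10% margin for the provider main effect takes 431 per group. The 44 may rest on inputs from its cited source, which are not shown.

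**The case against.** A reader might infer that the Protocol specifies a 3-month t-test of mode by severity and that this test has 54-69% power. The text does not support that. The 3-month t-test in 3.5.3.1 is named only for specialist versus non-specialist. Within severe women at 0.5 SD, that comparison has about 75-90% power after 10% loss, so for it the claim is broadly defensible. Mode moderation is planned as a mixed model over 3, 6 and 12 months, and Protocol 3.5.2 lists baseline depression among the possible covariates of its mixed models. Either feature could bring mode power near or above 80%.

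This stands, and it is why 54-69% is given as a conditional figure. It does not rescue the claim, because the plan states no correlation and no interaction calculation. Two cautions apply to the higher figures. Severity is itself a cut of entry EPDS, so the correlation that counts is what remains within severity groups. Averaging over visits also answers a question about the average effect, and assumes no loss beyond 10%, while Protocol 3.2 expects 20% by 12 months.

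It is also fair that 0.5 SD, the common SD and the two-level split are choices made here. The SAP aim uses three severity levels, and the documents give SDs of both 4.68 and 7.0. At 0.6 SD, mode power would be 70-84%.

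Finally, nothing in the documents says that a non-significant interaction will be read as equal effect. That is a risk created by the power claim, not a stated intention.

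**Conclusion.** The concern holds in a limited form. The claim of adequate power for medium-size heterogeneity is unsupported: the one calculation behind it is wrong for its own design (52% against a stated 80%) and is not an interaction calculation. Mode, the contrast that SAP Secondary Aim 2 names, is the weaker of the two. Its power is about 54-69% under the unadjusted 3-month assumptions, and runs up to 93% under the most favourable correlation considered. Provider type has 70-84% on the unadjusted basis.

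Two stronger readings should be avoided. The documents do not show that the planned mixed model must be underpowered, since that depends on correlations they leave out. Nor is the small in-person group the only cause: equal arms would still give 70% at 10% severe. The point affects a secondary aim and leaves the primary comparisons untouched.

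**What to change.** - **Protocol 3.5.3.1, calculation:** correct the 2.3-point sentence to about 52% power, or state 3.2 points for 80%.
- **Protocol 3.5.3.1, conclusion:** replace the adequacy claim with interaction figures at the planned allocation and their assumptions. Unadjusted at 3 months, 80% power is reached for about 0.57-0.68 SD for mode and 0.47-0.56 SD for provider. If the adjusted or mixed-model analysis is the intended one, give its figure with the assumed correlation.
- **SAP 3.4.2.3:** replace the sizing of 44 with the same figures.
- **Reporting:** present the arm-by-severity interaction as an estimate with its 95% CI, and state that a non-significant result is not evidence of equal effect in severe women.
- **Allocation text:** reconcile Protocol 2.8 (equal numbers in the four arms) and SAP 1.5 (equal in-person and telemedicine numbers) with the 268/958 plan.

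The cost is wording in two documents. No extra recruitment or data collection is needed. The stated power becomes less favourable.

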# 2 METHODS – Participants, Interventions and Outcomes

# 2.1. Participants and Setting.

N=1230 pregnant and postpartum women, aged ≥18, will be recruited from three study centers though their networks of clinics. Participants will be drawn from diverse and representative populations in Toronto, Chapel Hill, and Chicago. The flow chart (Figure 1) shows the process of recruitment and follow-up of participants in each hub. In Toronto, we will recruit from Sinai Health (SH), Women's College Hospital (WCH) and St. Michael's Hospital (SMH)—three major academic hospitals that are all affiliated with the University of Toronto, and our external referral networks. In North Carolina, we will recruit from three clinical sites affiliated with the University of North Carolina (UNC) Women's and Neuroscience Hospitals. In Chicago, we will recruit from fourteen affiliated obstetric and family medicine clinics. Our trained research assistants will approach all attending women or contact via phone for a screening. At one site (WCH), permission will first be required by a member of the participant's circle of care, will introduce the study and ask if she is interested in learning more. If the participant agrees, the trained research assistant will approach the participant in person or via phone for screen. Recruitment personnel will use established safety protocols (Appendix A - Safety Protocols and Forms). Inclusion and exclusion criteria are detailed in Table 5. Screening will take place inperson or over the phone, as determined by the referral pathway.

Table 5. Inclusion and Exclusion Criteria

INCLUSION	EXCLUSION

 
EPDS≥10
 
≥18 years
 
Pregnant up to 36 weeks or 4 to 30 weeks postpartum
 
Speaks English or (US sites) Spanish
 
	
 
Active suicidal intent (ideation and plan), active symptoms of psychosis or mania
 
Psychotropic medication dose or medication change within two weeks of enrollment or beginning treatment
 
Ongoing psychotherapy (no more than once every 8 weeks or during the duration of the intervention)
 
Active substance abuse or dependence
 
Severe fetal anomalies, stillbirth or infant death at time of enrollment for index pregnancy
 
Non-English, non-Spanish speakers
 

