#### 2.8. Randomization

All participants will be stratified by perinatal period (antenatal vs. postnatal) and then randomized within site to one of the four arms, unless restricted to two arms due to COVID-related institutional restrictions of in-person care (see section 2.2.3.2) and using a web-based randomization service as part of REDCap™. Randomization will occur only after informed consent has been obtained and all baseline measures have been completed and all inclusion/exclusion criteria verified with the participant. We will enroll equal numbers in each of the four intervention arms. This strategy allows sufficient power to determine whether NSPs are no less efficacious than specialists and telemedicine is no less efficacious than in-person treatment, respectively, in settings that collectively assure ethnic and racial diversity, as well as potential heterogeneity in age, variability in symptom severity as well as access to resources.

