## 3.2. Drop Out and Follow-Up Strategies

We expect 20% of participants to be lost to follow-up. This dropout rate is conservative and has been found in many similar trials using NSPs and specialist delivered PTs for perinatal depression in the US and Canada. Based on a Cochrane review, numerous research on study retention (e.g., ), and our previous experiences, it is realistic to expect a 12-month post-randomization follow-up rate of at least 80% when we incorporate the following strategies:

- (1) Participant Strategies: We will complete qualitative interviews at the participant's pace, allow flexibility with the interviews, design information material at a low reading level, and provide realistic expectations regarding study involvement. We will send quarterly newsletters to study participants with information that might be of interest or that participants may find useful, and reminders about questionnaire timelines (see SUMMIT Newsletter Template, Appendix E pg 103). A small token of appreciation will be provided to all mothers (\$15 USD/\$20 CAD gift card) per completed assessment. Upon completion of the 12-month questionnaire, participants will be entered in a raffle to receive a \$100 gift card. The raffle will be held for every 100 participants who complete the questionnaire. Upon completion of the child assessment, participants will be provided a \$40 token of appreciation. Participants reluctant to have RAs in their homes for the child assessment will have the option to complete the child assessment at the site hospital;
- (2) **Tracking Strategies**: REDCap™ will be used as a study-specific computerized tracking system to calculate follow-up dates. We will request permission from each participant for two secondary contacts (e.g., relative or friend) in the event that we lose contact with the participant. In the event that we are not able to reach the participant and we reach out to a secondary contact, no information about the participant will be released to the secondary contact (*see Secondary Contact Form, Appendix E Study Documents,* pg 83). We will verify and update contact information for the participant at each follow-up session. Email or telephone reminders will be sent to participants prior to each appointment or assessment;

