- **3.5.3.2. Perinatal Period.** This model will also test whether expectant mothers who receive antenatal treatment benefit more in terms of reduced depressive symptoms than mothers who receive postnatal treatment at 12-months post-randomization. A 2-group comparison with 200 per group and an assumed mean of EPDS score of 7.93 (SD=4.68) will provide 90% power, with an alpha of 0.05, to detect a mean change of 1.5 points. This allows us to detect a drop corresponding to a small effect size of 0.3 (i.e., a drop to mean 6.43 on the EPDS). The two groups' (antenatal vs. postnatal) EPDS scores at 3-months will be compared using a two-sided two-sample t-test. Change in EPDS scores over time (baseline and every 3 months, post-randomization) also will be compared using linear mixed models including the interaction between group and time. We will examine anxiety symptoms at 12-months post randomization in a linear mixed model controlling for relevant covariates including child age.

We will examine the hypothesis of whether the subset of mothers (up to 75% of the sample) who receive the antenatal treatment will benefit more in terms of improved child

outcomes at 6-24 months than mothers who receive postnatal treatment. A 2-group comparison of 238 per group (antenatal vs. postnatal) and an assumed mean on any Bayley IV raw subscale score of 100, SD=15 to assess child mental development will provide 80% power, with an alpha of 0.05 to detect a mean clinically-significant change of 3.0 units. Raw and standardized Bayley IV scores of the two groups' children (antenatal vs. postnatal) at 12 months will be compared using a two-sided, two-sample t-test.

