3.4.2. Secondary Analysis

3.4.2.1. Analysis for Secondary Aim 1: Anxiety Symptoms

In our secondary analysis, we are interested in **examining the primary questions for anxiety symptoms at 3-months post randomization.**

This aim is to show that NSP is non-inferior to SP. One t-test will be run to assess this and compare agents (is NSP non-inferior to SP). This aim is to also show that TM is non-inferior to in-person. Another t-test will be run to assess this and compare modes (is TM non-inferior to IP). We will require a sample of 774 participants and use a NIM of 10% for NSP compared to SP which translates to a mean EPDS difference of 0.871 based on the mean of 8.71 (SD=4.61)³⁷ and 10% dropout. On the other hand, a sample of 460 participants and a NIM of 13% will be required for TM compared to IP which translates to a mean difference of 1.142 based on the

mean of 8.71 (SD=4.61)³⁷ and 10% dropout. In addition, we will run a linear regression model with mode, agent, and a mode by agent interaction term to assess whether an interaction between mode and agent exists.

No interim analyses will be carried out.

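### The protocol adjusts the 12-month antenatal vs postnatal anxiety model for child age, but at that visit the two groups share no child ages

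*Protocol*

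**What the plan says.** Protocol 3.5.3.2 (Perinatal Period) compares women treated in pregnancy with women treated after birth. For anxiety it states: "We will examine anxiety symptoms at 12-months post randomization in a linear mixed model controlling for relevant covariates including child age". Table 5 of the protocol, repeated as Table 1 of the SAP, admits women who are "Pregnant up to 36 weeks or 4 to 30 weeks postpartum". Perinatal period is a stratification factor (Protocol 2.8), not a randomised one. Protocol 3.5.3.2 also refers to "the subset of mothers (up to 75% of the sample) who receive the antenatal treatment".

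Other sections treat the covariate differently. Protocol 3.5.2 lists child age among possible covariates only for the assessment of child outcomes. SAP 3.4.2.2 plans mixed models for antenatal vs postnatal depression and anxiety trajectories with a group-by-time interaction, and SAP 3.4.2.5 covers the same comparison at 12 months. Neither names child age.

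The only power statement for maternal symptoms in this part of the plan concerns the EPDS: "A 2-group comparison with 200 per group and an assumed mean of EPDS score of 7.93 (SD=4.68) will provide 90% power". The target there is a 1.5-point difference, tested at the 5% level. None is given for the anxiety model.

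**The concern.** At a fixed visit, child age is the visit time plus the woman's position relative to birth when she enrolled. Group is the sign of that same position. Both terms in the model therefore come from one quantity, and putting study time in the model does not separate them. Nobody enrols between 36 weeks of pregnancy and 4 weeks postpartum, so there is a hole exactly where the groups meet.

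The adjusted coefficient would be reported as the effect of treating before rather than after birth. It would in fact compare the groups at a child age that at least one of them never has at that visit. The answer would lean on the assumed shape of the age slope and carry a much larger standard error than the unadjusted difference. Because the protocol names the covariate and the SAP does not, the choice between the two models could also be made after the results are known.

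**Working it through.** **1. The plan's own figure.** With 200 per group, SD 4.68 and a difference of 1.5, SE = 4.68 × √(2/200) = 0.468 and 1.5/0.468 = 3.205. Two-sided power at alpha 0.05 is Φ(3.205 − 1.96) = 0.893, which agrees with the stated 90%. This is an EPDS figure without child age.

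**2. Child age at the nominal 12-month visit (52 weeks).**
- Antenatal: 52 minus the weeks from randomisation to birth. Birth follows randomisation, so the age is below 52 weeks. A woman enrolled at 36 weeks who delivers at 40 has a child aged 52 − 4 = 48 weeks.
- Postnatal: 52 + (4 to 30) = 56 to 82 weeks.
- Overlap: none. The gap is at least 4 weeks, or about 8 with term birth. This step needs only the eligibility windows.

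**3. Effect on the standard error.** Let p be the antenatal share, d the difference in mean child age and W the pooled within-group variance of child age. With residual variance held fixed, VIF = 1 + p(1 − p)d²/W, and the SE is multiplied by √VIF. Assumptions not in the documents are the enrolment distribution, delivery at 39.3 weeks (SD 1.5), p between 50% and 75%, and any visit delay.

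Worked case: uniform entry over 4–36 weeks' gestation and 4–30 weeks postpartum.
- Antenatal mean age = 52 − (39.3 − 20) = 32.7; variance = 32²/12 + 1.5² = 87.6.
- Postnatal mean age = 52 + 17 = 69; variance = 26²/12 = 56.3. So d = 36.3 and d² = 1,318.
- p = 0.50: W = 72.0, VIF = 1 + 0.25 × 1,318/72.0 = 5.58, factor 2.36.
- p = 0.75: W = 79.8, VIF = 1 + 0.1875 × 1,318/79.8 = 4.10, factor 2.02.

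Simulation reproduces both factors. Over other patterns it gives:

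| Entry pattern | Antenatal share | Visits | SE factor |
|---|---|---|---|
| Uniform, from 4, 8, 12 or 20 to 36 weeks; 4–30 weeks postpartum | 50% | on time | 2.36–2.45 |
| Same | 65% | on time | 2.22–2.49 |
| Same | 75% | on time | 2.02–2.40 |
| Skewed to late pregnancy and early postpartum | 50% | on time | 2.14–2.16 |
| Same | 75% | on time | 1.85–1.86 |
| U-shaped | 50–75% | on time | 1.75–2.02 |
| Uniform or skewed | 50–75% | late, mean 4 weeks | 1.64–2.18 |
| Everyone at the window limits (extreme bound) | 50–75% | on time | 1.43–1.60 |

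The top of the range comes from narrower windows. For uniform entry over 20–36 weeks' gestation and 4–16 weeks postpartum at 50%, d = 62 − 40.7 = 21.3, W = (23.6 + 12)/2 = 17.8, VIF = 1 + 0.25 × 453.7/17.8 = 7.4, factor 2.7.

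With visits late by a mean of 4 weeks, about 2% to 5% of antenatal children in the uniform and skewed patterns pass the youngest postnatal age.

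**4. On the anxiety scale.** SAP 3.4.2.1 gives SD 4.61 in its anxiety sample-size calculation. Protocol 3.2 expects at least 80% follow-up at 12 months: 0.80 × 1,230 = 984. At 75:25 the unadjusted SE is 4.61 × √(1/738 + 1/246) = 0.34. With child age under uniform entry it is 0.69 to 0.81.

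**5. Illustration on the EPDS inputs.** At 200 per group the split is 50:50, so the uniform-entry factor is 2.36 to 2.45. The ratio 3.205 falls to 1.36 or 1.31, and power from 89% to about 26–27%. This shows the scale only; it is not a figure for the anxiety model.

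**The case against.** The strongest reply is that this is one clause in the protocol, on an aim that the SAP calls exploratory, in a comparison that is not randomised, and that the SAP does not carry it over. That is correct. It limits the weight of the point, and no primary conclusion is touched. It does not remove the conflict between the documents.

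Several stronger readings are tempting, and the documents do not support them.

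- *A reader might infer that the standard error is more than doubled as a matter of fact.* That needs an enrolment distribution, which neither document gives. Several reasonable patterns fall below 2.
- *A reader might infer that separation is complete whatever happens.* It is exact only at nominal timing. SAP Table 2 marks the 12-month visit as extendable (Protocol Table 6 marks only the 3-month visit), and SAP Table 6 plans a sensitivity analysis on days to completion. Late visits can create a small overlap.
- *A reader might infer that the age slope is wholly untestable, or that the sign of the effect will depend on its form.* Child age varies within each group, so slope, curvature and equality of slopes can be examined there. Only behaviour across the gap cannot. The documents give no pattern of symptoms by child age from which a change of sign could be shown.
- *A reader might infer that antenatal rows before birth would be dropped because child age is undefined.* That depends on how the covariate is coded and which visits enter the model. Protocol 3.5.3.2 defines neither, and its sentence concerns symptoms at 12 months.

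**Conclusion.** The point holds. With child age in the model, the 12-month timing effect on anxiety can be obtained only by extending an assumed age slope across ages that the two groups do not share. This follows from the eligibility windows alone at nominal visit timing, and late visits change it little.

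The cost in precision is conditional: roughly a doubling of the standard error under near-uniform enrolment, about 1.6 to 2.7 times over plausible enrolment patterns and visit delays, and about 1.4 times at an extreme bound. The protocol clause is also out of line with Protocol 3.5.2 and with the matching SAP sections. This should be corrected, but it concerns a secondary, non-randomised comparison.

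**What to change.** 1. Remove child age from the antenatal vs postnatal maternal symptom models in Protocol 3.5.3.2. Keep it for child outcomes, as Protocol 3.5.2 has it.
2. Reconcile Protocol 3.5.3.2 with SAP 3.4.2.2 and 3.4.2.5, so that one covariate set is fixed for this comparison before analysis.
3. State in both documents that at 12 months the groups differ in time since birth by design, so the comparison is exploratory and cannot separate treatment timing from child age.
4. A comparison at matched child age is optional and descriptive only. Setting the antenatal 12-month visit against the postnatal 3- and 6-month visits exchanges the child-age difference for one of 6 to 9 months in time since randomisation, and the report must say so.

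The cost is a few sentences of protocol and SAP wording. No new data and no change to sample size are needed.
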